8.5.2.2 Definition absolute change and percent change from baseline (TP2)

The absolute change and percent change from baseline (TP2) is calculated in the same way as described above.

8.5.2.3 Decrease of (percent predicted) FEV₁ or FVC > 15% from baseline

A percent change decrease > 15% is defined for the following periods:

- During TP1: up to Month 6 for subjects who complete TP1 on treatment and up to EOT for subjects who discontinue study treatment during TP1.
- During TP2: up to EOT.
- Treatment-emergent (combining TP1 and TP2 data): up to EOT + 180 days.

8.5.3 Analysis

Spirometry outputs will be produced using the SAF (for TP1 and for TP1+TP2) and SAF-TP2 (for TP2).

Observed values, changes from baseline and percent changes from baseline of FEV₁ and FVC will be summarized by visit and treatment group, during TP1 using the FAS, during TP2 using the FAS-TP2, and combining TP1 and TP2 for each post-baseline assessment up to EOS using the FAS.

For percentage changes from baseline, summary statistics will be derived from the geometric mean of the ratio to baseline, and from the geometric mean of the ratio to predicted value at baseline for the percentage change expressed as percent of predicted baseline. Geometric mean will be computed and transformed into a percentage change by using the transformation $x \rightarrow ((x-1) \times 100)$ as described in Section 8.9.2.

The CV of the geometric mean will also be presented [see Section 8.9.2 for calculation].

All outputs defined above will be repeated for percent predicted FEV₁ and FVC.

Summary statistics will be produced showing the number of subjects with a treatment-emergent decrease of at least 15% from baseline for FEV₁ and FVC and percent predicted FEV₁ and FVC. Decreases during TP1 and during TP2 will be summarized as well.

Spirometry data will be listed using the SAF.

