8.5.2 Variables

8.5.2.1 Definition absolute change and percent change from baseline (TP1)

The absolute change from baseline for FEV₁, FVC, percent predicted FEV₁ and percent predicted FVC is calculated as follows:

- Change from baseline = FEV₁ at post-baseline visit – FEV₁ at baseline
- Change from baseline = FVC at post-baseline visit – FVC at baseline

Percent change from baseline for FEV₁, FVC, percent predicted FEV₁ and percent predicted FVC is calculated as follows:

- Percent change from baseline = (FEV₁ at post-baseline visit – FEV₁ at baseline) / FEV₁ at baseline × 100
- Percent change from baseline = (FVC at post-baseline visit – FVC at baseline) / FVC at baseline × 100

Percent change from baseline expressed as percent of predicted baseline for FEV₁ and FVC is calculated as follows:

- Percent change from baseline = $(\text{FEV}_1 \text{ at post-baseline visit} - \text{FEV}_1 \text{ at baseline}) / \text{predicted FEV}_1 \text{ at baseline} \times 100$
- Percent change from baseline = $(\text{FVC at post-baseline visit} - \text{FVC at baseline}) / \text{predicted FVC at baseline} \times 100$

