8.9.2 Analysis

Biomarker data will be analyzed using the FAS and data up to the EOS visit.

For biomarkers standard summary statistics for absolute values, absolute change and percent change from baseline will be presented, by visit and treatment group.

Summary statistics of percentage changes will be derived from the geometric mean of the ratio to baseline. Because geometric mean of data is equivalent to $\exp(\text{mean of log-transformed data})$, the geometric mean of the ratio to baseline is equivalent to $\exp(\text{mean of } (\log[\text{post-baseline}] - \log[\text{baseline}]))$. Geometric mean of the ratio to baseline will be transformed into a percentage change by using the transformation $x \rightarrow ((x-1) \times 100)$.

The CV of the geometric mean will be derived as:

$$100 \times \sqrt{\exp\left((SD_{\log})^2\right) - 1}$$

Note that anti-cardiolipin antibodies are only collected at baseline and therefore only the baseline summaries will be presented for this parameter.

Biomarkers will be listed using the FAS.

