	
• Section 6.5: added description of study discontinuation related to COVID-19 pandemic.• Section 6.8.6 (Previous and concomitant therapies): Description of background SLE therapies by ATC and PT was replaced by a description by categories mentioned in the protocol and PT• Section 6.9.2 (Compliance): Clarifications on derivation of compliance when the kit is not returned or was replaced• Section 7 (Efficacy analyses): subject random effect was removed from all models• Number of replicated for multiple imputation was reduced from 500 to 100 for all analyses using MI• Section 7.2.6.9 (Dose-response analysis): MCP-Mod analyses to be performed were clarified and piece of code added• Section 7.4.5 (Time to first severe flare up to Month 6), section 7.4.6 (Time to first flare up to Month 6): Log-rank test was removed• Section 7.5.1 (Sustained mSLEDAI-2K response): Added the definition of subjects with enough assessments to be assessed for this endpoint• Section 7.5.10 (Change from baseline to each post-baseline assessment up to Month 12 in prednisone or equivalent dose): Clarification of the analysis windows: If a subject has a visit recorded after Month 6 but the Month 6 visit was not done, Month 6 visit will be replaced by Day 180.• Section 7.6.1 (FACIT-Fatigue): Month-3 analysis timepoint was added following protocol amendment (protocol version 4.0)• Section 7.6.4 (SF 36v2™): The health transition score will only be described at Month 12, as it rates the current state compared to one year before• Section 7.6.5 (Lupus QoL): Scoring details were described as per scoring manual• Section 7.6.6 (mucocutaneous and musculoskeletal score): The sum of the mucocutaneous and musculoskeletal score will also be described• Section 8.5 (Spirometry): Formula for percent change from baseline expressed as percent of predicted baseline for FEV1 and FVC was corrected• Section 8.5 (Spirometry): Geometric mean and CV for percent change from Baseline were added following dry-run 1 review• Section 8.8 (Echocardiography sub-study): Sample size increased from 125 to 175 following protocol amendment (protocol version 4.0)• Section 8.8 (Echocardiography sub-study): All abnormalities will be described, not only clinically relevant ones• Section 8.9 (Biomarkers): List of selected biomarkers (quantitative variables) to be described was added. All other biomarkers (qualitative variables) will only be listed• Section 8.9 (Biomarkers): Derivation of geometric mean for percent change from baseline was clarified

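### SAP 8.5.3 summarizes spirometry change, scaled to predicted, with a statistic that drops the subject's own baseline and so is not the variable defined in 8.5.2.1

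*SAP*

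**What the plan says.** SAP section 8.5.2.1 lists three spirometry measures: absolute change, ordinary percent change (change over the subject's baseline), and a third introduced with "Percent change from baseline expressed as percent of predicted baseline for FEV₁ and FVC is calculated as follows". The formula for the third, given separately for FEV1 and FVC, is post-baseline minus baseline, divided by the predicted value at baseline, times 100. Section 8.5.2.2 applies the same definitions from the Treatment Period 2 baseline.

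Section 8.5.3 sets the summary statistics for percentage changes. For the ordinary percent change they come from the geometric mean of the ratio to baseline. For the third measure they come "from the geometric mean of the ratio to predicted value at baseline for the percentage change expressed as percent of predicted baseline". In both cases the geometric mean x is converted by (x − 1) × 100, with a reference to section 8.9.2, and the CV of the geometric mean is also shown.

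Section 8.9.2, written for biomarkers, says "Summary statistics of percentage changes will be derived from the geometric mean of the ratio to baseline" and spells the ratio out as the exponential of the mean of log post-baseline minus log baseline. The numerator is therefore the post-baseline value.

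The revision history for SAP version 3.0 records "Formula for percent change from baseline expressed as percent of predicted baseline for FEV1 and FVC was corrected", and in the same version the addition of the geometric mean and CV for spirometry. The change logs for versions 4.0 and 5.0 list nothing that reconciles the two sections.

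**The concern.** The definition and the summary carry the same name but are different quantities. If predicted replaces baseline as the reference in the 8.9.2 ratio, the subject's observed baseline no longer enters. A line labelled as change from baseline would then show lung function level relative to predicted.

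Change in FEV1 and FVC from baseline is a listed safety endpoint (SAP section 8.1.1). The mislabelled line would show a spurious decrease in subjects whose baseline is below predicted. In subjects above predicted it would show a spurious increase that can hide a real fall. The CV would describe the spread of levels between subjects, not the spread of changes.

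Two further consequences follow. Because the observed baseline is absent, change from the Treatment Period 1 baseline and change from the Treatment Period 2 baseline would coincide at the same visit for the same subjects, apart from any update of the predicted value. And 8.5.3 repeats its outputs for percent predicted: if predicted is held at its baseline value, the absolute change in percent predicted equals the 8.5.2.1 variable, so one set of outputs could show two values for one quantity.

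**Working it through.** The plan states no numerical result here, so there is no figure to reproduce. The check compares the two formulas.

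**Formulas.** For one subject, with base, post and pred (predicted at baseline):

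- Defined variable (8.5.2.1): V = 100 × (post − base)/pred.
- Summary as written (8.5.3 with the 8.9.2 convention): S = 100 × (post/pred − 1).
- Difference: S − V = 100 × (base/pred − 1).

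This identity needs no assumption. The two agree only when baseline equals predicted.

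**Worked case** (assumed pred 3.00 L, base 2.40 L, post 2.16 L, a 10% fall):

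- V = 100 × (2.16 − 2.40)/3.00 = −8%.
- S = 100 × (2.16/3.00 − 1) = −28%.
- Offset = 100 × (2.40/3.00 − 1) = −20 points.

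**Range of assumed baselines** (each cell is V / S, in %):

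| Baseline, % of predicted | No change | 5% fall | 10% fall |
|---|---|---|---|
| 70 | 0 / −30 | −3.5 / −33.5 | −7 / −37 |
| 80 | 0 / −20 | −4 / −24 | −8 / −28 |
| 90 | 0 / −10 | −4.5 / −14.5 | −9 / −19 |
| 100 | 0 / 0 | −5 / −5 | −10 / −10 |
| 110 | 0 / +10 | −5.5 / +4.5 | −11 / −1 |

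At 110% of predicted, a 5% fall changes sign.

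**The other possible numerator.** Section 8.5.3 does not write the numerator out. If it were the change itself, the ratio (post − base)/pred would be −0.08 in the worked case and 0 for no change. Neither has a logarithm, so the geometric mean does not exist. A gain giving +0.08 would convert to (0.08 − 1) × 100 = −92%.

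**CV.** Section 8.9.2 gives CV = 100 × √(exp(s²) − 1), with s the SD on the log scale. Assume SD of log change 0.06, SD of log(base/pred) 0.10, 0.15 or 0.20, and change independent of baseline:

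- Ratio to baseline: s = 0.06, CV = 6.0%.
- Ratio to predicted: s² = 0.06² + 0.10² = 0.0136, CV = 11.7%; 0.06² + 0.15² = 0.0261, CV = 16.3%; 0.06² + 0.20² = 0.0436, CV = 21.1%.

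**Comparison between arms.** With 325/5 = 65 subjects per arm and the same assumed SDs, chance imbalance in baseline percent predicted alone gives the arm difference in mean log ratio a standard error of √(2/65) × 0.10, 0.15 or 0.20, or about 1.8, 2.6 or 3.5 log points (hundredths on the log scale). Variation in true change contributes √(2/65) × 0.06, about 1.1.

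**The case against.** The best counter-argument is that 8.5.3 leaves the numerator unstated and that a third construction would work: the geometric mean of 1 + (post − base)/pred, converted by (x − 1) × 100. It returns 0% for no change and −8.0% in the worked case, matching 8.5.2.1. A programmer starting from the already defined variable might use it, and the revision history suggests that change from baseline was the target. On that view the sentence is loosely worded and needs only a clarification. But this form is not a ratio to the predicted value and is written nowhere in the SAP. No reading of the text as it stands yields the defined variable. If it is what the sponsor intends, the SAP still has to say so.

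Other points stand, and limit the size. No spirometry values appear in the documents, so the 70 to 110% range is unanchored, and the offset is zero at 100%. The line is descriptive. The same section tabulates observed values, absolute change and ordinary percent change, so a real fall would show in adjacent rows. Section 8.5.2.3 does not say which percent change the 15% decrease counts use, but those counts are made per subject and this group statistic does not enter them. An offset common to all arms largely cancels between arms, though chance imbalance remains.

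The CV comparison above is with the ratio to baseline, which is a different variable. The like-for-like comparator is the CV of 1 + (post − base)/pred. In simulated groups of 65 (assumed mean log change −0.03 with SD 0.05, and SD 12 points for percent predicted, at mean baselines of 80, 90 and 100% of predicted) that CV was 3.8 to 4.6%, against 11.1 to 15.5% for the ratio to predicted. The conclusion on the CV does not change.

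**Conclusion.** The concern holds. Followed as written, 8.5.3 puts a level relative to predicted under a change-from-baseline label. The error is exactly 100 × (baseline/predicted − 1) for each subject. That identity rests only on reading the 8.5.3 ratio as post-baseline over predicted, which is the convention of the section it refers to.

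The sizes rest on assumed baselines: at 70 to 110% of predicted, the error runs from −30 to +10 points. The CV figures also rest on assumed SDs. The damage is limited to one descriptive FEV1/FVC summary, in Treatment Period 1, Treatment Period 2 and combined. Efficacy analyses, absolute change, ordinary percent change, the 15% decrease counts and the adverse events of special interest are not affected. It should be corrected because it concerns a listed safety endpoint and would print a wrong number.

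**What to change.** In SAP section 8.5.3, summarize (post-baseline − baseline)/predicted at baseline × 100 with arithmetic statistics (mean, SD, median, quartiles), which are already the default in section 9.1. Restrict the geometric mean and its CV to the ratio to baseline. If post-baseline over predicted is also to be shown, label it as deviation from predicted, not as change from baseline. If the sponsor prefers to keep a geometric form for this variable, the ratio must be written out so that it reproduces the 8.5.2.1 definition.

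The cost is one SAP sentence and one table program. No new data are needed.

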8.6 Electrocardiography

The 12-lead ECG measurements and qualitative ECG findings (e.g., rhythm, ectopy, conduction and morphology) are provided by the ECG central reader, along with the overall interpretation of the ECG (Normal/Abnormal).

ECG Holter monitoring data and findings are also provided by a central reader.

8.6.1 Measurements

12-lead ECG is measured at visits defined in the visit and assessment schedule [see Appendix 12.1].

The following parameters will be evaluated: HR (bpm), PR (ms), QRS (ms), QT (ms), QTc (ms), and any ECG findings. QTc (ms) is calculated according to Bazett's and Fridericia's formula. Data is received in derived form by the vendor.

A time window approach will be applied to the ECG data [as defined in Section 5.4.4].

ECG Holter monitoring is performed for 24 hours at Visit 2 (Randomization).

8.6.2 Variables

8.6.2.1 Change from baseline in 12-lead ECG

Change of ECG measurements is derived on the day of first study drug intake, on the day of re-initiation and generally from the baseline (in TP1) to each pre-dose assessment at any visit during the conduct of the study. Changes are derived for any ECG parameter provided by the vendor (mean HR, PR interval, QRS duration, QT interval, QTcB and QTcF interval).

The intra-day change is defined for the day of first study drug intake and the day of re-initiation, by hour:

$$\text{Hourly intra-day change} = \text{Value at hourly post-dose assessment} - \text{value at pre-dose assessment.}$$

ECG values at the pre-dose assessment must have been assessed on the day of first study drug intake / day of re-initiation, otherwise they are considered to be missing. Some subjects might stay longer in hospital than the expected 6 hours. Intra-day changes are also calculated for assessments performed later than 6 hours after first study drug intake.

Changes compared to a derived baseline value are defined as:

$$\text{Change} = \text{Value at post-baseline visit (pre-dose)} - \text{derived baseline value.}$$

The derived baseline value is defined as the last valid value measured prior to first study drug intake in TP1 (by date and time). For HR, the mean ECG HR is used to derive the baseline value. For the remaining ECG parameters (PR interval, QRS duration, QT

interval, QTcB and QTcF interval) aggregate values are provided by the ECG central reader that are used to derive the baseline value.

Changes from baseline are also derived based on the TP2 baseline.

8.6.2.2 Notable abnormalities (12-lead ECG)

Table 11 Notable abnormalities in ECG parameters

Analysis parameter	Analysis variable(s)	Analysis criterion
QTcB (ms) and QTcF (ms)	Analysis value	- Value > 450 and ≤ 480 (male), > 470 and ≤ 480 (female) - Value > 480 and ≤ 500 - Value > 500 and ≤ 520 (female) - Value > 500 (male), > 520 (female)
	Change from baseline	- Increase from baseline > 30 and ≤ 60 - Increase from baseline > 60
	Analysis value and change from baseline	- Value > 450 and increase from baseline > 30 and ≤ 60 - Value > 450 and increase from baseline > 60
Heart rate (bpm)	Analysis value	- Value < 40
PR duration (ms)	Analysis value	- Value > 200
	Change from baseline	- Increase from baseline > 20
	Analysis value and change from baseline	- Value > 200 and increase from baseline > 20

bpm = beats per minute; ECG = electrocardiogram; QTcB = QT interval corrected for heart rate using Bazett's formula; QTcF = QT interval corrected for heart rate using Fridericia's formula.

Notable ECG abnormalities are derived as described in [Table 11](#) and defined for the following periods:

- Day of first study drug intake (up to 24 hours after first study drug intake).
- During TP1: up to Month 6 for subjects who complete TP1 on treatment and up to EOT for subjects who discontinue study treatment during TP1.
- During TP2: up to EOT.
- Treatment-emergent (combining TP1 and TP2 data): up to EOT + 180 days.

Values and changes derived above will be used to characterize abnormalities.

8.6.2.3 Morphological ECG abnormalities/findings (12-lead ECG)

Morphological ECG findings are defined for:

- Day of first study drug intake (up to 24 hours after first study drug intake).
- During TP1: up to Month 6 for subjects who complete TP1 on treatment and up to EOT for subjects who discontinue study treatment during TP1.

- During TP2: up to EOT.
- Treatment-emergent (combining TP1 and TP2 data): up to EOT + 180 days.

Due to the automatic transfer of data from the hospital to the vendor all date and time information should be complete. In the unlikely event of missing date and time, the missing information is imputed in the same way as the date and time information for TEAEs.

8.6.2.4 Holter ECG

Due to the HR-lowering effect of cenerimod on the first day of study drug intake the baseline Holter value and all other post-baseline values are derived dependent on the time of the first study drug intake. Baseline is defined as the average HR prior to first study drug intake.

Hourly averages of the HR after baseline are also calculated based on the time of the first study drug intake.

Example:

If the start time of first study drug intake is 8:22:00 am, the mean HR in the interval [7:22:00 am (or start of recording); 8:21:59 am] is considered as the baseline value and the mean HR in the interval [8:22:00 am; 9:21:59 am] is considered as the first hourly interval. The mean HR is calculated for 24 intervals (if data available).

For each Holter ECG, a cardiologist will provide an overall interpretation (Normal/Abnormal) and will describe potential findings.

Each finding reported for the Holter ECG performed on the day of first study drug intake is considered to be treatment-emergent (up to 24 hours after the start of recording).

Absolute changes of the mean hourly HR are defined as follows:

$$\text{Changes of the mean hourly HR} = \text{mean hourly HR at hour X} - \text{mean hourly HR at baseline}$$

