8.6.3 Analysis

8.6.3.1 12-lead ECG

All ECG outputs will be summarized using the SAF and SAF-TP2.

Standard summary tables will be produced, by time point, for any ECG parameter provided by the vendor on the day of first study drug intake by treatment group. A similar summary table will be produced by study visit, for TP1, for TP2 and for TP1 and TP2 combined. Figures over time will be produced to support the summary tables.

The incidence of ECG outliers / notable ECG abnormalities and morphological ECG findings will be summarized for the periods defined above.

A subject will be counted only once in the most severe category of a given parameter. An abnormality is only counted as treatment-emergent if the criterion itself and all more severe criterion for the same parameter were not already present at baseline.

Percentages will be based on the number of subjects at risk, i.e., those not meeting the criterion or a more severe criterion for the same parameter at baseline (or having a missing baseline value) and having at least one post-baseline value for a given parameter. For criteria that are based on an increase from baseline, subjects with a missing baseline value are not included in the number of subjects at risk.

For QTcB and QTcF, a shift table from baseline to worst value post-baseline will be produced based on the abnormalities.

The incidence of ECG outliers/notable ECG abnormalities and morphological ECG findings will be summarized for TP2 as well. Outputs will be displayed in the same way as described above, based on 6 treatment groups using the SAF-TP2.

ECG data (parameters and findings) will be listed by treatment group, subject and visit using the SAF.

All post-treatment notable abnormalities will be flagged and qualitative abnormalities (as transferred by the ECG central reader) will be listed using the SAF.

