- (4) Echocardiography will be performed at Visit 1 (Screening) preferably within 30 days prior to Randomization for all subjects and at Visit 8 (Month 6) in approximately 175 subjects, as part of the ancillary study. In the event of premature study treatment discontinuation during TP1 (i.e., before Visit 8), echocardiography will be performed at pEOT visit and will not be required at Visit 8.
- (5) A chest X-ray that has been performed within 6 months prior to Screening can be used (in this case, there is no need to repeat the chest X-ray at Screening).
- (6) At each pre-dose assessment, SBP/DBP measurements will be performed twice in the supine position.
- (7) On Day 1 and at Re-initiation visit, SBP/DBP assessment and 12-lead ECG will be done pre-dose and hourly until 6 h post-dose; after 6 h, subjects may be discharged if they meet the discharge criteria, otherwise SBP/DBP assessments and 12-lead ECG will be performed hourly until discharge criteria are met. If discharge criteria are not met after 12 h, the subject must be permanently discontinued. At all other visits, only pre-dose SBP/DBP assessments and 12-lead ECG will be performed.

- (8) On Day 1 and at Re-initiation visit, 24-hour ECG Holter should start before dosing. The subject must return to the site on Day 2 (Visit 2a) / Re-initiation (Visit I2) for removal of the device after 24-hour recording.
- (9) On Day 1 and at Re-initiation visit, PK samples will be collected 6 hours after dosing. At Visits 3, 4, 5, and 8, PK samples will be collected pre-dose. At pEOT visit, in the event of premature treatment discontinuation during TP1 (i.e., before Visit 8) and at EOS visit, PK samples will be collected at any time during the visit and will not be required at Visit 8.
- (10) Hematology assessments, including coagulation tests will be performed at each visit until EOS, except FU2, FU3 and FU3a, and FU3b visits.
- (11) Serum pregnancy tests will be performed at Screening and EOS. Urine pregnancy tests will be performed at all other visits. To ensure compliance, the study personnel must remind WOCBP at each visit to use the methods of contraception defined for this study from the Screening visit until 6 months after taking the last dose of study treatment.
- (12) All AEs and SAEs occurring after signing the ICF and up to 6 months after study treatment discontinuation must be reported.

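### Every finding on the Day 1 Holter is labelled treatment-emergent from the start of recording, so findings that precede the first dose are counted in the descriptive table of Holter findings

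*SAP*

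**What the plan says.** **The Holter rule.** SAP 8.6.2.4: "Each finding reported for the Holter ECG performed on the day of first study drug intake is considered to be treatment-emergent". The parenthesis that follows sets the window as "up to 24 hours after the start of recording".

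**When recording starts.** SAP 12.1, footnote 8: "On Day 1 and at Re-initiation visit, 24-hour ECG Holter should start before dosing". Section 8.6.1 gives the length: "ECG Holter monitoring is performed for 24 hours at Visit 2 (Randomization". The schedule shows no Holter before Day 1.

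**How the same section treats pre-dose time.** For heart rate, 8.6.2.4 takes the average before first intake as baseline. In its worked example, with a tablet at 8:22, the interval "7:22:00 am (or start of recording); 8:21:59 am] is considered as the baseline value".

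**Other Day 1 safety data.** Section 8.6.2.2 defines the 12-lead window as "Day of first study drug intake (up to 24 hours after first study drug intake", and 8.6.2.3 does the same for morphological findings. Sections 8.2.1 (adverse events) and 8.7.1.3.1 (blood pressure) also tie Day 1 to first intake.

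**Baseline exclusion.** Section 8.6.3.1 on the 12-lead ECG: "An abnormality is only counted as treatment-emergent if the criterion itself and all more severe criterion" for that parameter were absent at baseline, with percentages based on subjects at risk. Section 8.7.1.3.2 has the equivalent rule for blood pressure.

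**Output.** Section 8.6.3.2 summarizes coded Holter findings by treatment group. Episode counts are left out of the table and kept in the listing. No baseline exclusion is stated.

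**The concern.** Every recording made according to footnote 8 contains some pre-dose time. The heart-rate analysis calls that time baseline; the findings rule, in the same section, calls it treatment-emergent. Two kinds of finding are mislabelled: those seen only before the tablet, and those already present before it that continue afterwards.

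Section 8.6.2.4 gives the first-day heart-rate-lowering effect of cenerimod as its reason for tying Holter values to the time of the first dose. A findings table for that day is useful if it shows what is new after the dose, by arm. Pre-existing findings, balanced on average by randomization, raise the incidence in all five arms, placebo included, and make the arms look more alike. In a safety table that is the unhelpful direction.

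**Working it through.** The plan states no rate, power or sample size for Holter findings, so there is no figure of its own to reproduce. The check is a comparison of rules, then an illustration of size.

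**1. The rules side by side**

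| Day 1 data | Window tied to | Pre-existing excluded? |
|---|---|---|
| Adverse events (8.2.1) | time of first intake | yes, onset before dosing is non-emergent |
| 12-lead notable abnormalities (8.6.2.2, 8.6.3.1) | first intake | yes |
| 12-lead morphological findings (8.6.2.3) | first intake | rule in 8.6.3.1 is worded for graded criteria |
| Blood pressure abnormalities (8.7.1.3) | first intake | yes |
| Holter hourly heart rate (8.6.2.4) | time of first intake | pre-dose mean is the baseline |
| Holter findings (8.6.2.4) | **start of recording** | **no** |

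Only the last row starts its clock before the drug. No other section of the SAP changes that.

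**2. What the window covers.** If recording starts h hours before dosing, 24 hours from the start holds h pre-dose hours and 24 − h post-dose hours: for h = 1, 1 and 23. A 24-hour recording ends at the same moment, so the window covers all of it.

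**3. Effect on counted rates.** Let q be the share of subjects with the finding already present before dosing, equal across arms by randomization, and p the probability of a new post-dose finding in the others.

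- Counted rate = q + (1 − q)p
- Counted risk difference = (1 − q)(p_dose − p_placebo)

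Neither q nor p is in the documents. Assuming p = 5% on placebo and 20% on a dose (true difference 15 points, true ratio 4.0):

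| q | Placebo | Dose | Difference (points) | Ratio |
|---|---|---|---|---|
| 0% | 5.0% | 20.0% | 15.0 | 4.00 |
| 5% | 9.75% | 24.0% | 14.25 | 2.46 |
| 10% | 14.5% | 28.0% | 13.5 | 1.93 |
| 20% | 24.0% | 36.0% | 12.0 | 1.50 |
| 30% | 33.5% | 44.0% | 10.5 | 1.31 |

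Example at q = 10%: 0.10 + 0.90 × 0.05 = 0.145; 0.10 + 0.90 × 0.20 = 0.280.

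With rarer findings, assumed 2% and 8% (true difference 6.0 points, ratio 4.0), q = 5%, 10%, 20% and 30% give differences of 5.7, 5.4, 4.8 and 4.2 points and ratios of 1.83, 1.46, 1.22 and 1.13. The ratio falls much faster than the difference, so both need to be read.

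**4. How large could q be?** For isolated events at a constant rate with 24-hour background incidence B, the chance of one in h pre-dose hours is 1 − (1 − B)^(h/24). For h = 1:

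- B = 5%: 0.2%
- B = 20%: 0.9%
- B = 50%: 2.9%

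Taking B = 5% to match the placebo rate above, q = 0.21% gives 5.2% against 20.2%, a ratio of 3.88: almost no change. Values of q of 5% or more therefore need findings that persist or recur, and so show both before and after the tablet.

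**The case against.** The best defence is that little depends on this rule. The findings table is descriptive, has no test, and is not titled treatment-emergent in 8.6.3.2. Holter findings are not named in the safety endpoint list in 8.1.1. The exclusion in 8.6.3.1 is written for graded numeric criteria, which a cardiologist's reading of one continuous recording does not have. The SAP also counts an adverse event with no recorded time on the day of first intake as emergent (8.2.1.1), so counting everything follows an inclusive convention that drops no event. The documents do not show that the reader's findings carry onset times. A strict exclusion could also hide a rhythm finding that becomes more frequent after dosing.

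Most of this stands, and it limits the point. It does not make the rule coherent: 8.2.1.1 covers events whose time is unknown, whereas 8.6.2.4 also labels findings known to precede the tablet. The points about onset times and worsening shape the fix.

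A reader might infer three stronger things, which the documents do not support:

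- *The last post-dose hour is discarded.* The window covers the whole planned 24-hour recording. For hourly heart rate, 8.6.2.4 already allows for intervals without data.
- *The first-dose heart-rate analysis is diluted.* It is anchored to the time of intake with a pre-dose baseline, and is untouched.
- *A dose comparison is biased, or findings are attributed to the drug.* No Holter contrast is tested, and treatment-emergent is a timing label, not a causal claim.

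**Conclusion.** The rule is wrong as written, within a small scope. It labels findings that precede the first dose treatment-emergent, which is out of line with how the SAP treats other Day 1 safety data and with its own Holter heart-rate baseline. The effect is limited to the descriptive table of coded findings: incidence overstated in every arm, the risk difference multiplied by (1 − q), and the ratio drawn toward 1.

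The direction is certain for any q above zero if the post-dose rates differ; the size is not known. It rests on q, which the documents do not give, on q being equal across arms, and on the assumed post-dose rates. For isolated events in a short pre-dose stretch the distortion is negligible. It is material only if persistent or recurrent findings are common.

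**What to change.** In 8.6.2.4, define a Day 1 Holter finding as treatment-emergent only if its onset is at or after the first dose and it is not already present in the pre-dose segment. Carry this into 8.6.3.2, since changing the label alone would leave the counts as they are, with these rows:

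- **Pre-dose findings**, tabulated as baseline.
- **Findings present both before and after dosing**, in their own row so that worsening stays visible.
- **New post-dose findings**, as treatment-emergent. Basing percentages on subjects without the finding before dosing matches 8.6.3.1 and, in the illustration, returns 5% against 20% at any q.
- **Findings with no onset time**, labelled as findings during the Day 1 recording and not as treatment-emergent.

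Footnote 8 also schedules a Holter at re-initiation, which the rule in 8.6.2.4 does not mention; the same edit can say how those findings are classified.

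The cost is SAP wording, extra table rows and use of onset times where the reader reports them. The small downside is that untimed findings move to a non-emergent row. If no times exist, the change reduces to an accurate label and needs no new data.
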